6.2.2 Partial Response (PR)

PR requires the following:

- At least a 50% decrease in sum of the product of the diameters (SPD) of up to six of the largest dominant nodes or nodal masses. These nodes or masses should be selected according to all of the following: they should be clearly measurable in at least 2 perpendicular dimensions; if possible they should be from disparate regions of the body; and they should include mediastinal and retroperitoneal areas of disease whenever these sites are involved.
- 2. No increase should be observed in the size of other nodes, liver, or spleen.

- 3. Splenic and hepatic nodules must regress by ≥ 50% in their SPD or, for single nodules, in the greatest transverse diameter.
- 4. With the exception of splenic and hepatic nodules, involvement of other organs is usually assessable and no measurable disease should be present.
- 5. Bone marrow assessment is irrelevant for determination of a PR if the sample was positive before treatment. However, if positive, the cell type should be specified (e.g., large-cell lymphoma or small neoplastic B-cells). Patients who achieve a CR by the above criteria, but who have persistent morphologic bone marrow involvement will be considered partial responders. When the bone marrow was involved before therapy and a clinical CR was achieved, but with no bone marrow assessment after treatment, patients should be considered partial responders.
- 6. No new sites of disease should be observed.
- 7. Typically FDG-avid lymphoma: for patients with no pretreatment PET scan or if the PET scan was positive before therapy, the post-treatment PET should be positive in at least one previously involved site.

Variably FDG-avid lymphomas/FDG-avidity unknown: for patients without a pretreatment PET scan, or if a pretreatment PET scan was negative, CT criteria should be used.

6.2.3 Stable Disease (SD)

- SD requires the following:
- 1. A patient is considered to have SD when he or she fails to attain the criteria needed for a CR or PR, but does not fulfill those for progressive disease (see Relapsed Disease [after CR]/Progressive Disease [after PR, SD]).
- 2. Typically FGD-avid lymphomas: the PET should be positive at prior sites of disease with no new areas of involvement on the post-treatment CT or PET.

Variably FDG-avid lymphomas/FDG-avidity unknown: for patients without a pretreatment PET scan or if the pretreatment PET was negative, there must be no change in the size of the previous lesions on the post-treatment CT scan.

6.2.4 Relapsed Disease (after CR) or Progressive Disease (after PR or SD)

- Lymph nodes should be considered abnormal if the long axis is more than 1.5 cm regardless of the short axis. If a lymph node has a long axis of 1.1 to 1.5 cm, it should only be considered abnormal if its short axis is more than 1.0. Lymph nodes ≤ 1.0 x ≤ 1.0 cm will not be considered as abnormal for relapse or progressive disease.
- 2. Appearance of any new lesion more than 1.5 cm in any axis during or at the end of therapy, even if other lesions are decreasing in size. Increased FDG uptake in a previously unaffected site should only be considered relapsed or progressive disease after confirmation with other modalities. In patients with no prior history of pulmonary lymphoma, new lung nodules identified by CT are mostly benign. Thus, a therapeutic decision should not be made solely on the basis of the PET without histologic confirmation.
- 3. At least a 50% increase from nadir in the SPD of any previously involved nodes, or in a single involved node, or the size of other lesions (e.g., splenic

or hepatic nodules). To be considered progressive disease, a lymph node with a diameter of the short axis of less than 1.0 cm must increase by \geq 50% and to a size of 1.5 x 1.5 cm or more than 1.5 cm in the long axis.

- 4. At least a 50% increase in the longest diameter of any single previously identified node more than 1 cm in its short axis.
- 5. Lesions should be PET positive if observed in a typical FDG avid lymphoma or the lesion was PET positive before therapy unless the lesion is too small to be.

Response	Definition	Nodal Masses	Spleen, Liver	Bone Marrow
CR	Disappearance of all evidence of disease	 (a) FDG-avid or PET positive prior to therapy; mass of any size permitted if PET negative (b) Variably FDG-avid or PET negative; regression to normal size on CT 	Not palpable, nodules disappeared	Infiltrate cleared on repeat biopsy; if indeterminate by morphology, immunohistochemistry should be negative
PR	Regression of measuable disease and no new sites	≥ 50% decrease in SPD of up to 6 largest dominant masses; no increase in size of other nodes (a) FDG-avid or PET positive prior to therapy; one or more PET positive at previously involved site (b) Variably FDG-avid or PET negative; regression on CT	≥ 50% decrease in SPD of nodules (for single nodule in greatest transverse diameter); no increase in size of liver or spleen	Irrelevant if positive prior to therapy; cell type should be specified
SD	Failure to attain CR/PR or PD	 (a) FDG-avid or PET positive prior to therapy; PET positive at prior sites of disease and no new sites on CT or PET (b) Variably FDG-avid or PET negative; no change in size of previous lesions on CT 		
Relapsed disease or PD	Any new lesion or increase by ≥ 50% of previously involved sites from nadir	Appearance of a new lesion(s) > 1.5 cm in any axis, ≥ 50% increase in SPD of more than one node, or ≥ 50% increase in longest diameter of a previously identifed node > 1 cm in short axis Lesions PET positive if FDG-avid lymphoma or PET positive prior to therapy	> 50% increase from nadir in the SPD of any previous lesions	New or recurrent involvement

Table 5: Response and Progression from RRCML adopted from Cheson, et al.

6.2.5 Progression Free Survival

Progression-free survival (PFS) is defined as the duration of time from start of treatment to time of progression. PFS will be reported at 1 and 3 years after the start of treatment.

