2.2 Secondary Objectives & Endpoints

2.2.1 Evaluate the safety of the combination of romidepsin and lenalidomide.

The endpoint will be the frequency and severity of toxicity events using the NCI CTCAE v 4.03.

2.2.2 Further evaluate efficacy of the combination of romidepsin and lenalidomide.

The endpoints will be progression-free survival (PFS) and overall survival (OS) at 1 and 3 years after start of treatment as well as the duration of response from start of therapy, defined per Cheson criteria.

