5.0 Study Procedures

Table 4: Time and Events

Study Period	Baseline		On Treatment ¹⁰ (1 cvcle = 28 days	5)	Off Treatment Visit	Follow-Up ¹⁴
Procedures & Assessments	Screening ⁹	Day 1 of Each cycle ¹¹ (±3 days)	Day 8 and 15 of Each cycle ¹¹ (-1 to +3 days)	Response Assessments	28-Days Post Last Dose ¹³	Survival Status
Informed consent	х					
Medical history	х					
Physical exam ¹	х	х			х	х
ECOG status	Х	Х			Х	Х
Imaging ^{2, 12}	X ²			X ¹²	Х	
Hematology Labs ^{18, 9}	х	х	Х			
Chemistry Labs ^{3, 9}	Х	Х	Х			
Pregnancy test ⁴	X4		X ¹⁹			
EKG⁵	х					
Bone marrow biopsy ¹⁷	х			Х	Х	
Tissue for research ⁶	Х					
REMS® program ⁷	Х	Х				
Adverse events ⁸	Х	Х			х	
Concomitant medications	Х	Х				
Creatinine Clearance Check ²⁰		Х				
Lenalidomide treatment			X ¹⁵			
Romidepsin treatment			X ¹⁶			

¹ Physical exam should include vitals (blood pressure, heart rate, temperature, respirations), height (baseline only), and weight.

² Tumor assessment with diagnostic quality CT (chest, abdomen, pelvis; neck if clinically indicated) with or without contrast imaging within 28 days prior to registration; in addition, NM PET/CT is not required but encouraged prior to starting therapy (with or without contrast).

³ Lactate dehydrogenase (LDH), magnesium (Mg) and comprehensive metabolic panel (CMP) including albumin, alkaline phosphatase, ALT(SGPT), AST(SGOT), BUN, creatinine, electrolytes (sodium, potassium, calcium, chloride, bicarbonate), glucose, and total bilirubin.

⁴ Either urine or serum pregnancy test required within 7 days prior to registration for WOCBP; additional pregnancy testing required throughout the treatment period as outlined in the REMS® program.

⁵ EKG required within 28 days of registration (for eligibility) and then as clinically indicated thereafter.

- ⁶ If available, archived tissue from a previous biopsy is required for exploratory studies (patients who do not have available/adequate tissue may still enroll). See Section 9 for details.
- ⁷ All study participants must be registered into the mandatory REMS® program, and be willing and able to comply with the requirements.
- ⁸ SAE's will be collected from the time of consent until 30 days after treatment discontinuation.
- ⁹ All screening procedures are required within 28 days prior to registration unless otherwise indicated. Chemistry and Hematology labs are required within 14 days of registration.

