- ¹⁰ Cycle 1 to begin within 14 days after registration; Treatment will continue up to 1 year unless any of the criteria in Section 4.4 are met.
- ¹¹ One cycle = 28 days ± 3 days for start of cycle. Day 8 and 15 each have a window of -1 to +3 days
- ¹² Response will be assessed with diagnostic quality CT (chest, abdomen, pelvis; neck if clinically indicated) with or without contrast imaging after cycles 3 and 6 (±7 days), and then every 6 months (±7 days). Response may be assessed more often if clinically indicated. Although not required, we encourage the use of NM PET/CT performed at baseline and repeated along the same schedule throughout (with or without contrast).
- ¹³ All patients should have a visit approximately 28 days (+/- 7 days) post-last dose of study treatment.
- ¹⁴ Once off treatment, patients will be followed clinically every 3 months (±7 days) for up to 1 year from start of study treatment, then every 6 months (±14 days) up to a total of 3 years (or until death, whichever comes first) for survival endpoints.
- ¹⁵ Lenalidomide will be given at a dose of 25 mg PO daily on days 1-21 of each cycle (followed by a 7 day break prior to the start of the next cycle). Patients will be given a medication diary to complete, which will be reviewed with a member of the study team at visits.
- ¹⁶ Romidepsin will be administered intravenously on days 1, 8, and 15 of each cycle. The dose for the first 2 cycles (6 doses total) will be 10 mg/m²; in some cases, patients may be escalated to a dose of 14 mg/m² for remaining cycles (see Section 4.1.1 for specific criteria). A window is allowed for romidepsin infusion visits (within ±3 days of day 1, and within -1 to +3 days of days 8 and 15).
- ¹⁷ Bone marrow biopsy will be done within 90 days of registration if clinically indicated, per treating physician's discretion. In patients with known bone marrow involvement at baseline, a bone marrow biopsy will be performed after the patient achieves a CR.
- ¹⁸ Complete blood count with differential will be performed weekly for the first 2 cycles, every other week for cycles 3-6, and at the start of each cycle thereafter.
- ¹⁹ Day 15 of each cycle only.

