6.2 Efficacy Endpoints

Response and progression will be evaluated using the 2007 Revised Response Criteria for Malignant Lymphoma (RRCML) as defined by Cheson, et al.[43] See Table 5 for a summary of the follow definitions:

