6.2.6 Overall Survival

Overall survival (OS) is defined as the duration of time from start of treatment to time of death, up to three years from the start of study treatment. OS will be reported at 1 and 3 years after the start of treatment.

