10.2 Secondary Endpoints

To evaluate the safety of the combination of romidepsin and lenalidomide, the endpoint will be the frequency and severity of toxicity events using the NCI CTCAE v 4.03. All

adverse events will be summarized as to type, severity, frequency, timing and attribution. Descriptive frequencies and proportions will be used for this analysis.

To further evaluate efficacy of the combination of romidepsin and lenalidomide, the endpoint will be progression-free survival (PFS) and overall survival (OS) at 1 and 3 years after start of treatment as well as the duration of response from start of therapy, defined per Cheson criteria. Kaplan-Meier curves will be determined for progression-free survival and overall survival and the one- and three-year point on this curve, along with 90% confidence limits. Duration of response will be summarized by descriptive statistics in responders (mean, median, range).

To evaluate the delay to cytotoxic chemotherapy, the endpoint will be time to first cytotoxic chemotherapy (TTFCC) from start of treatment. This will be summarized by descriptive statistics (mean, median, range).

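### Section 6.2.5 ends PFS at progression and does not count death, so the 1- and 3-year rates, read literally, are time-to-progression rates

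*Combined protocol and SAP*

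**What the plan says.** The combined protocol and SAP defines PFS once, in 6.2.5: "Progression-free survival (PFS) is defined as the duration of time from start of treatment to time of progression". It is to be reported at 1 and 3 years. The next definition, in 6.2.6, does name death: "Overall survival (OS) is defined as the duration of time from start of treatment to time of death".

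Progression itself is described in 6.2.4 and Table 5 through new or growing lesions and marrow involvement. A death is not a progression under those criteria.

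On the analysis, 10.2 says "Kaplan-Meier curves will be determined for progression-free survival and overall survival", read off at 1 and 3 years with 90% limits. It gives no event or censoring rule. Sections 2.2.2 and 10.2 list PFS and OS and then add "as well as the duration of response from start of therapy, defined per Cheson criteria". Section 6.2 adopts the 2007 revised lymphoma criteria for judging response and progression, and does not mention PFS there.

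On assessments, Table 4 footnote 12 schedules CT after cycles 3 and 6, "and then every 6 months (±7 days). Response may be assessed more often if clinically indicated", with no end date. The Follow-Up column of Table 4 is labelled "Survival Status". As far as the extracted table can be read, it marks physical examination and ECOG status but no imaging. Section 4.5 provides clinic visits to 3 years from start of treatment, or to death.

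**The concern.** PFS at 1 and 3 years is a named secondary efficacy endpoint. Eligible patients are aged 60 or over, or are younger with a CIRS score of 6 or more or judged ineligible for cytotoxic chemotherapy (3.1.3). Section 1.4 notes that the older patients often have comorbidities, and 11.11 makes three treatment-related deaths a trigger for suspending accrual. Deaths without documented progression are therefore foreseeable.

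An analyst who follows 6.2.5 would not count those deaths. An analyst who follows the usual meaning of the name would. The same data could then give two different PFS rates, and the one that follows the written definition could never be the lower of the two.

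**Working it through.** **The plan's own figure.** The only precision figure stated is for the response rate: 1.96 × 0.5/√20 = 1.96 × 0.1118 = 0.219, given as 0.22 in 10.1. It reproduces. There is no numerical PFS assumption to check.

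**Direction.** Suppose deaths without progression are censored. With untied event times, the numbers at risk are the same under both rules. The progression-or-death curve is then the time-to-progression curve multiplied by (1 − 1/r) for each death without progression up to the landmark, where r is the number at risk at that death. So:

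- a death by the landmark makes the literal rate higher, unless the curve is already at zero;
- a death after the landmark leaves that landmark unchanged.

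**Example at n=20 (assumed data).** Eight progressions by month 12, ten by month 36, full follow-up:

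| Deaths without progression | 1 year: literal vs progression-or-death | 3 years: literal vs progression-or-death |
|---|---|---|
| none | 60.0% vs 60.0% | 50.0% vs 50.0% |
| one, month 2 | 57.9% vs 55.0% | 47.4% vs 45.0% |
| three, months 2, 4, 8 | 55.1% vs 45.0% | 42.9% vs 35.0% |
| one, month 14 | 60.0% vs 60.0% | 49.1% vs 45.0% |

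Check on the second row: 11/19 = 57.9%, and 57.9% × 19/20 = 55.0%.

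**Size under constant hazards (assumed).** Let the median time to progression be m = 12 or 24 months, and the net annual risk of death without progression be d = 5% or 10%.

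- Literal rate: exp(−h₁t), with h₁ = ln 2/m per month.
- Progression-or-death PFS: exp(−(h₁+h₂)t), with h₂ = −ln(1−d)/12. This equals the literal rate × (1−d) at 1 year and × (1−d)³ at 3 years.

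| m | Landmark | Literal | PFS, d=5% | PFS, d=10% | Excess (points) |
|---|---|---|---|---|---|
| 12 mo | 1 year | 50.0% | 47.5% | 45.0% | 2.5 to 5.0 |
| 24 mo | 1 year | 70.7% | 67.2% | 63.6% | 3.5 to 7.1 |
| 12 mo | 3 years | 12.5% | 10.7% | 9.1% | 1.8 to 3.4 |
| 24 mo | 3 years | 35.4% | 30.3% | 25.8% | 5.1 to 9.6 |

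The 3-year rows assume that disease is assessed to 3 years.

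**How often it would arise.** With m = 12, the share dying without progression in year 1 is h₂/(h₁+h₂) × [1 − exp(−12(h₁+h₂))] = 3.6% or 7.3%. Among 20 patients that is 0.7 or 1.5 expected deaths. The chance of at least one is 1 − (1−p)²⁰ = 52% or 78%.

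**Against sampling error.** The 90% half-width for a proportion near one half is 1.645 × √(0.25/20) = 0.18.

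**The case against.** The strongest reply is that the gap is one of wording. The name PFS carries death with it by convention, and the reference to the Cheson criteria in 2.2.2 and 10.2 could be read as covering the whole list of endpoints, not only duration of response. That reading cannot be excluded on grammar. But the documents reproduce no PFS definition from that source, 6.2 invokes it only for response and progression, and 6.2.5 supplies an explicit definition of its own. At best the sections are in tension, which still calls for a correction.

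It is also fair that the consequence is small. No test or decision rests on PFS. The response rate, the futility stop and the toxicity rules do not use it, and OS at the same landmarks counts every death up to 3 years. This stands and limits the weight of the point.

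Three stronger readings are tempting and are not supported:

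- *The reported rates are bound to be too high.* The plan does not say how deaths are handled, and the excess calculated here depends on censoring them. Leaving them in the denominator as never progressing would make it larger (60% against 45% at 1 year in the three-death example). Counting them as events would remove it. Deaths after the landmark do not matter to that landmark.
- *Scans stop when treatment ends, so 3-year PFS is meaningless.* No section says this. The inference rests on blank cells in an extracted table, whereas footnote 12, 2.1 and 10.1 give 6-monthly imaging with no end date. What can be said is that the two do not clearly match.
- *Duration of response has the same error.* Section 6.2.7.1 is also silent on death, but that is a missing detail, and no error follows from it here.

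**Conclusion.** The definition gap is real and nothing elsewhere in the documents closes it. With deaths without progression censored, the planned 1- and 3-year rates estimate time to progression. The excess over progression-or-death PFS is zero or upward: about 2.5 to 7 points at 1 year and, if disease is assessed that long, about 2 to 10 points at 3 years. Those figures rest on assumed constant hazards and assumed rates, because the documents supply none.

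At 1 year the excess is smaller than the sampling error with 20 patients. However, the confidence limits would show sampling error and would not show this shift. The point concerns the meaning of one descriptive secondary endpoint and does not touch the trial's primary conclusion. It is worth correcting because the correction is precise and nearly free.

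**What to change.** In 6.2.5 and 10.2, define the PFS event as first documented progression or death from any cause, whichever comes first, and censor patients alive without progression at their last disease assessment. Alternatively, keep the present rule and rename the endpoint time to progression.

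Also reconcile the Follow-Up column of Table 4 with footnote 12, so that it is clear how long disease status is assessed, and report 3-year PFS only if it is assessed to 3 years.

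The definition needs text changes only, since 4.5 already follows patients for death to 3 years. If disease assessment is not meant to run that long, the cost is either the added assessments or the loss of the 3-year PFS figure. The other downside is that reported PFS may be slightly less favourable.

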6.2.6 Overall Survival

Overall survival (OS) is defined as the duration of time from start of treatment to time of death, up to three years from the start of study treatment. OS will be reported at 1 and 3 years after the start of treatment.

6.2.7 Duration of Response

6.2.7.1 Duration of overall response:

The duration of overall response is measured from the time measurement criteria are met for CR or PR (whichever is first recorded) until the first date that recurrent or progressive disease is objectively documented (taking as reference for progressive disease the smallest measurements recorded since the treatment started).

The duration of overall CR is measured from the time measurement criteria are first met for CR until the first date that recurrent disease is objectively documented.

6.2.7.2 **Duration of stable disease:**

Stable disease is measured from the start of the treatment until the criteria for progression are met, taking as reference the smallest measurements recorded since the treatment started.

6.2.8 Time to first cytotoxic chemotherapy

Time to first cytotoxic chemotherapy (TTFCC) is defined as the time from start of study treatment to time of first dose of anti-neoplastic cytotoxic chemotherapy that is administered to treat lymphoma. This does not include corticosteroids, antivirals, or chemotherapeutic agents used for either non-neoplastic diseases or other malignant processes (not lymphoma).

6.3 Exploratory Endpoints

6.3.1. Evaluate the use of NM PET/CT vs. CT imaging in PTCL.

The endpoint will be a review of the utilized imaging modalities during treatment as a tool of response assessment. All patients will have CT imaging for enrollment and response assessment time points as outlined in Table 4. When both imaging modalities are chosen for a patient (per treating investigator's discretion), response assessment will be compared.

6.3.2 Validate a new prognostic model for newly diagnosed PTCL.[41]

The endpoint will be clinical biomarkers including age, race, histology, and stage as obtained at enrollment. A points based system will be used to correlate with recently developed prognostic model.

6.3.3 Investigate the tumor immunohistochemical profile to identify potential biomarkers associated with prognosis and treatment response.

The endpoint we be comparison of immunohistochemical profiles with treatment outcomes on archived tissue samples. A tumor microarray on paraffin-embedded tissue samples will be constructed for comparison. Tissue will be obtained from patients who have tissue available at baseline for these studies. If tissue is not available, it will not preclude patients from participating. However, for those with tissue available, it is a mandatory component of participation.

7.0 Adverse Events

7.1 Adverse Event Monitoring

Adverse event data collection and reporting, which are required as part of every clinical trial, are done to ensure the safety of subjects enrolled in the studies as well as those who will enroll in future studies using similar agents. Adverse events are reported in a routine manner at scheduled times during a trial. All adverse events will be reported on the appropriate eCRF. Additionally, certain adverse events must be reported in an expedited manner to allow for optimal monitoring of patient safety and care.

All patients experiencing an adverse event, regardless of its relationship to study drug, will be monitored until:

- the adverse event resolves or the symptoms or signs that constitute the adverse event return to baseline
- any abnormal laboratory values have returned to baseline
- there is a satisfactory explanation other than the study drug for the changes observed
- death

